- 4) Documented attainment of a 10 mmHg reduction in SBP at 6 months, as in Outcome 1, but assessed using home BP measurements, when available. As per guidelines, a set of 12 or more home measurements (counting no more than 2 in the morning and 2 in the evening of each day) within any given 1 week time period will count as a completed Home Measurement Protocol¹². The average SBP and DBP measurements within the most recent completed Home Measurement Protocol within 180 days of the index date (e.g., 6 months after enrollment) will then be used as the attained BP, regardless of subsequent clinic measurements or subsequent random home measurements. If no completed Home Measurement Protocol is available within 180 days of the index date, the most recent clinic measurement will be used. Note that a documented Home Measurement Protocol can only be attained in Arm 1, as home measurements will not be accessible in Arm 2.
- 5) Other BP Control outcomes defined as ((SBP<140 mmHg and DBP<90 mmHg) OR (SBP<130 and DBP<80) OR 10 mmHg reduction), assessed using the baseline measurement (self-reported OR last clinical measurement prior to randomization from the electronic health record) and subsequent measurements (clinical measurements OR clinical + home measurements) at a specified time-point (6 OR 12 OR 18 months) or using a time-to-control approach.
- 6) Patient reported outcomes including various aspects of satisfaction with the HBPM device and BP management, including quality of shared decision-making and patient activation.
- 7) Visit frequency. We will analyze the number of ambulatory care visits during the 6 month follow up period; we will also analyze the number of visits made before attainment of the first in-control BP.
- 8) Medication intensification. We will analyze the proportion of clinical visits with high BP (SBP>140 mmHg or DBP>90 mmHg) after which a BP medication was added.

Pre-specified subgroups: The following subgroups are pre-specified:

- Baseline Age: 20-44 vs 45-64 vs. 65+ years
- Sex: Male vs. Female vs. Other vs. Missing
- Race/Ethnicity: Non-Hispanic White vs. Non-Hispanic Black vs. Non-Hispanic Asian vs. Hispanic (any race) vs. Other/Multiple vs. Missing
- Subjective Social Status, measured through online survey at baseline, using MacArthur Scale for SES (not the “Community” version)⁹: Upper vs. Middle vs. Lower tertile, defined within our recruited sample of participants

Analysis Plan

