Overview: Our primary analyses will test two independent hypotheses: that SBP reduction (outcome 1, defined above) differs by study arm, and that promotion of the HBPM device (outcome 2) differs by study arm. Subgroup analyses and exploratory outcomes will also be analyzed, as described below.

Primary BP control analysis: For analysis of this outcome, which is continuous (defined above), we will use a random effects linear model, including a random effect for clinic and a fixed effect for a 3-level variable that indicates whether the clinic is participating in a concurrently-running cluster-randomized quality improvement trial (Not participating vs. Full Support MAP intervention^{13,14} vs. Self-Guided MAP intervention^{13,14}).

Primary patient satisfaction analysis: The Net Promoter Score (NPS) is calculated from the proportions of Promoters and Detractors, as described above. To assess the influence of treatment assignment and other exposures on the NPS, we will first define the 3-level outcome classifying each participant as a Promoter, a Passive, or a Detractor, then fit a random effects multinomial logistic model for the independent effect of the exposure on this outcome. The model will include the same random and fixed effects specified for the primary BP control analysis. Expected proportions in each outcome group by treatment assignment will then be obtained using standardization. Finally, the NPS scores for each group, as well as the between-group difference in the score, with 95% confidence intervals for each, will be calculated as linear combinations of the adjusted proportions, and a p-value calculated assuming a null hypothesis of no between-group difference in the NPS.

Subgroup analyses: We will produce subgroup-specific analyses of the primary outcomes for each of the pre-specified subgroups, and test for heterogeneity by including the appropriate interaction terms in the models described above, with an omnibus test for each of the 4 grouping variables. Subgroups that include fewer than 100 study participants or with missing values for the subgrouping variable will be omitted from the omnibus test and results presentation. P-values for within-subgroup treatment effects will be reported only if the omnibus test is statistically significant at P<0.05.

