Multiple imputation for missing data: Our general approach to missing data will be multiple imputation. While our primary BP control outcome is defined to minimize loss to follow up and missing data, it is still possible that follow up will be missing if EHR linkage fails. If this occurs (and in general for other analyses), we will use a multiple imputation strategy. This approach will be optimized by the requirement for completion of baseline surveys before randomization occurs. It is likely that our primary patient satisfaction outcome will be missing in a sizable proportion of patients, since it will require patients to log back into our system and fill out an additional survey. Again, we will handle this situation with multiple imputation. In addition to multiple imputation under the standard assumption that data are missing at random (conditional on observed covariates and outcomes), we will also implement sensitivity analyses using imputation under plausible missing-not-at-random scenarios.

Data and Safety/Interim Monitoring: Given the minimal risk nature of the intervention (both arms are considered standard of care), no formal interim monitoring is required. All study staff are CITI-trained, and will be on the alert for unanticipated adverse effects; if such effects are identified, UCSF study staff will notify our IRB and all study sites as needed to minimize risk for participants in the study.

Sample size justification: With 2000 patients randomized (1:1 ratio, 1000 standard vs. 1000 Smartphone-linked), we will have 80% power to distinguish very small standardized treatment effects of only 0.125 standard deviations (SDs). For example, if the standard deviation of SBP reduction is 8, we would have 80% power to distinguish a reduction of 11 mmHg from 10 mmHg in SBP reduction between the two groups. We have not attempted a power analysis for the Net Promotor outcome given the complexity of the calculated score.

References

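### Heterogeneity by age and subjective social status is tested only on three unordered groups; adding a continuous interaction would make the exploratory test more sensitive to a steady trend at little cost

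*Combined protocol and SAP*

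**What the plan says.** Under Pre-specified subgroups (Measurements), age enters as "Baseline Age: 20-44 vs 45-64 vs. 65+ years". Subjective social status is "measured through online survey at baseline, using MacArthur Scale for SES", and is then cut into "Upper vs. Middle vs. Lower tertile, defined within our recruited sample of participants".

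Under Subgroup analyses (Analysis Plan), heterogeneity is tested through interaction terms in the primary models, "with an omnibus test for each of the 4 grouping variables". The same paragraph drops small or missing categories ("Subgroups that include fewer than 100 study participants") from the omnibus test and the presentation, and sets a reporting condition: "P-values for within-subgroup treatment effects will be reported only if the omnibus test is statistically significant at P<0.05".

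No linear, trend or continuous interaction is specified for either variable. The paragraph on multiple hypothesis testing classes the subgroup analyses as exploratory. No power is given for any heterogeneity test.

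**The concern.** Both variables are ordered, and the randomization plan requires baseline data to be complete before assignment, so the scores should exist for everyone randomized. Three groups discard the variation within each group. An omnibus test on those groups also ignores their order and, in the SBP model, spends two degrees of freedom where a linear term spends one.

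A benefit that rises or falls steadily with age or social position is a natural pattern to look for with a Smartphone-linked device. The planned test is inefficient for it, and the same test decides whether within-subgroup p-values are shown. Age is named in Aim 3; social status is not.

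Two smaller features also favour a continuous term. Participants aged 18-19 are eligible but belong to no listed age band. And if the youngest band has fewer than 100 members, those participants leave the age test altogether.

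**Working it through.** **The plan's own figure.** Sample size justification: "With 2000 patients randomized (1:1 ratio, 1000 standard vs. 1000 Smartphone-linked"), with "80% power to distinguish very small standardized treatment effects of only 0.125 standard deviations (SDs"). With 1000 per arm and two-sided alpha 0.05 (assumed; the plan gives no number for the main test), power = Φ(0.125 × √(1000/2) − 1.96) = Φ(0.835) = 79.8%. The stated 80% reproduces. There is no heterogeneity power to reproduce.

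**Inputs from the plan.** N = 2000, 1:1 allocation, example outcome SD of 8 mmHg, alpha 0.05 for the omnibus test.

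**Assumptions.** The effect modification is linear, and the modifier distributions are as listed below.

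**Formulas.** Let γ be the change in treatment effect (mmHg) per SD of the modifier.

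- Continuous interaction, 1 df: noncentrality λ = N γ² / (4 × 8²).
- Three groups, 2 df: noncentrality R² × λ, where R² is the share of modifier variance lying between the groups.
- Power = P(noncentral χ² with d df > critical value); the critical value is 3.84 for 1 df and 5.99 for 2 df.

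**Reference case.** For 80% power at 1 df, λ = (1.960 + 0.842)² = 7.85. For tertiles of a normal modifier, the outer thirds have means ±1.091 SD, so R² = (2/3) × 1.091² = 0.793 and R²λ = 6.22.

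| Test of the same linear trend | Noncentrality | df | Power |
|---|---|---|---|
| Continuous, linear | 7.85 | 1 | 80.0% |
| Three groups, 1-df trend score | 6.22 | 1 | 70.4% |
| Three groups, omnibus (as planned) | 6.22 | 2 | 60.1% |
| Continuous, 3-knot spline | 7.85 | 2 | 70.9% |

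The loss is 19.9 points, about half from grouping and half from the second degree of freedom. A simulation (N=2000, SD 8, 4000 runs) gave 79.9%, 71.0% and 60.5% for the first three rows.

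**Other assumed modifiers, linear test at 80%.**

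| Assumed modifier | R² | Planned test | Loss (points) |
|---|---|---|---|
| Uniform, tertiles | 0.889 | 65.4% | 14.6 |
| Age mean 50-60, SD 12-15, cuts at 45 and 65 | 0.776-0.822 | 59.1-61.8% | 18.2-20.9 |
| Status on an assumed 10-step scale, mean 5.5-6, SD 1.5-2.0 | 0.762-0.825 | 58.3-61.9% | 18.1-21.7 |
| Age mean 65, SD 10 | 0.700 | 54.4% | 25.6 |

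In the last row about 2% of the sample is under 45, roughly 46 of 2000 at 2.3%. The rule on fewer than 100 participants would then reduce the age test to two levels and 1 df.

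**Dependence on the slope (normal tertiles).**

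| γ, mmHg per SD | λ | Linear, 1 df | Planned, 2 df | Loss (points) |
|---|---|---|---|---|
| 1.0 | 2000/256 = 7.81 | 79.8% | 59.9% | 19.9 |
| 0.5 | 1.95 | 28.7% | 18.3% | 10.4 |
| 0.25 | 0.49 | 10.8% | 8.0% | 2.7 |

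**Non-linear patterns (normal tertiles, omnibus test at 80%).** If only the middle group differs, the linear test has about 5% power. If only the top group differs, it has 67%.

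**Satisfaction outcome.** The multinomial model has two coefficients per interaction term. A joint test therefore has 2 df for a linear modifier and 4 df for either three groups or a 3-knot spline. With the linear test at 80% (λ = 9.63), three groups give 0.793 × 9.63 = 7.64 on 4 df, which is 58% power.

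**The case against.** Pre-specified categories with an omnibus interaction test are conventional, and they match Aim 3, which asks for outcomes within subgroups. The analyses are exploratory. Failing the omnibus test withholds only within-subgroup p-values; subgroup estimates are still produced for every eligible category. No primary conclusion, error rate or sample size depends on this test. All of that stands, and it limits the weight of the point.

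Three stronger readings are tempting, and the documents do not support them.

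- *The plan forfeits 20 points of power as a fixed cost.* That needs a linear trend, a roughly normal modifier and a slope near 1 mmHg per SD, as large per SD as the whole 1 mmHg difference the trial is sized to detect. The plan gives neither the modifier distributions nor an expected slope, and with weaker trends the loss shrinks to a few points.
- *A linear test should replace the omnibus test and control reporting.* Nothing in the plan establishes that the pattern is linear, and a linear test alone can do far worse than the planned test when only the middle group differs.
- *The social-status tertiles will be badly unequal.* Ties on a coarse scale could cause this, and no tie rule is stated. But the number of steps is not given in the text available, the survey wording sits in an attachment not included there, and the split depends on the assumed distribution and tie rule.

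**Conclusion.** The point holds as a modest gap in sensitivity. For a steady trend in the SBP model, the planned test loses about 15-22 percentage points against a linear interaction that has 80% power. The assumed older age distribution (mean 65, SD 10) loses more. The figure falls to about 10 points at 0.5 mmHg per SD and about 3 at 0.25. These sizes rest on linearity, assumed modifier distributions, N=2000 with complete data, and the plan's example SD of 8 mmHg. A 3-knot spline recovers about half of the loss in the reference case at the same 2 df as the planned SBP test. This is an optional, low-cost improvement to an exploratory analysis. It is not an error and does not affect the primary conclusions.

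**What to change.** Add to Subgroup analyses:

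1. For age in years and for the social-status score as recorded, pre-specify an arm-by-continuous interaction, either linear or a 3-knot restricted cubic spline, and say which.
2. Report it beside the categorical omnibus test, and keep the categories for displaying estimates.
3. For the satisfaction outcome, either test the interaction on the derived Net Promoter Score difference or state the joint test on the multinomial coefficients (2 df linear; 4 df for a spline or the current groups).

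It would also help to state how tied status scores are assigned to tertiles.

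The cost is a few sentences of plan text and no new data. The downsides are one extra exploratory test per variable for each primary outcome, and that a linear term alone would miss a U-shaped pattern. Keeping the omnibus test, or choosing the spline, guards against the latter.

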Uncontrolled BP is the leading preventable cause of death in the US after smoking, causing nearly 400,000 deaths per year¹. While effective medications are available to control BP, multiple rounds of medication adjustment and intensification are typically required, and BP control is often not achieved^{2,3}. The usual configuration of healthcare delivery – periodic and relatively infrequent office visits with a physician – is not ideal for achieving BP control quickly and efficiently^{4,5}. One promising approach to enhancing clinic-based BP management is to support home BP monitoring by patients⁶. Home BP monitoring technology has advanced substantially in recent years particularly in terms of linkage with Smartphones via Bluetooth, which enables use of associated Smartphone applications. Smartphone applications enable a wide variety of functions potentially useful for BP goal attainment, including reminders to measure BP, recording and displaying measurements, interpretation of measurements (e.g., goal attained, BP dangerously high, etc), and facilitating communication of measurements with treating clinicians. It is unclear, however, if this technological advancement helps patients achieve BP control. The PCORnet Home Blood Pressure Monitoring (BP HOME) Study is an individual-level randomized controlled trial that will compare the effectiveness of Smartphone-linked versus standard HBPM cuffs for helping patients with uncontrolled hypertension achieve a reduction in systolic blood pressure.

Aims

- 1) To compare the effectiveness of Smartphone-linked versus standard home BP monitors for helping patients with uncontrolled hypertension achieve a reduction in SBP.
- 2) To assess patient-reported outcomes including satisfaction with the HBPM device and various aspects of BP management
- 3) To assess the outcomes within subgroups based on age, sex and race/ethnicity.

Hypotheses

Patients with uncontrolled hypertension who receive a Smartphone-linked HBPM will have a larger average reduction in SBP at 6 months compared to those who receive standard HBPM, and will be more likely to promote use of the device to a friend.

Study Design

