Attachment D provides the text of the online surveys we will administer.

EHR data (all available data through end of follow-up will be extracted in the following domains)

Basic demographics

Diagnoses

Encounter characteristics

Provider characteristics

Blood pressure

Medications

Lab results

Death indicator

The EHR data analysis section, below, provides additional detail.

HBPM device data (all available measurements made during follow up, for Arm 1 only)

Blood pressure

Heart rate

Primary BP control outcome: The following pre-specified outcome will be used for the primary test of comparative effectiveness:

- 1) Reduction in SBP at 6 months. Reduction is defined by the absolute difference between the eligibility SBP (collected from the patient at the time of eligibility assessment), and the SBP measured at the most recent outpatient clinical encounter 6 months after enrollment. If more than 1 measurement is recorded during a single clinical encounter, the lower/lowest will be used.

Primary patient satisfaction outcome: The following pre-specified outcome will be used for the primary test of patient satisfaction:

- 2) Net Promotor Score. This score is assessed by asking a single question about likelihood of recommending the device to a friend, with options from 1-10 (10 being extremely likely). As per published methods^{7,8}, persons indicating 9 or 10 are considered "Promotors"; persons indicating 7 or 8 are "Passives"; and persons indicating 1-6 are

“Detractors”. The score is calculated by taking the percent of Promotors and subtracting the percent of Detractors, yielding a score for each group ranging from -100 to 100. Note that an identical score could theoretically be produced for a group with either a relatively high proportion of Promotors and Detractors, or a relatively low proportion of both.

Exploratory outcomes: The following pre-specified secondary outcomes will also be measured and analyzed. These include alternative measures of BP control, other patient-reported outcomes, and process measures intermediate along the causal pathway to BP control.

- 3) Documented attainment of a 10 mmHg reduction in SBP from baseline to 6 months, as defined above.

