In response to PCORnet's emphasis on ensuring access to health care interventions for vulnerable populations, we plan an exploratory post-hoc analysis examining any disparities in enrollment in BP HOME, particularly by race and ethnicity. Black and Hispanic/Latinx patients are underrepresented in clinical trials and health care research generally, and specifically within hypertension research. This is particularly worrisome given that these subgroups experience disproportionate burdens of negative sequelae of hypertension, including coronary artery disease, stroke, and chronic kidney disease. Further, the interaction between social determinants of health (SDH), Black race and Hispanic ethnicity, and participation in interventional trials is not well understood.

We plan to study the interaction between self-identified race, self-identified ethnicity, and various indicators of social determinants of health, measured at both the census tract and individual patient level, to understand their effects upon enrollment in BP Home. To accomplish this, participating BP Home sites will analyze all persons invited to join BP Home

and analyze predictors of enrollment. BP Home sites will consider different predictors depending on their availability; e.g., OCHIN may consider social determinants of health they have specified based on patient address and also at the individual patient level, while other sites may have different types of predictors. Sites will generally keep individual-level data on non-enrolled patients local and do analyses through their honest broker teams, sharing only model results (aggregated).

Multiple hypothesis testing: The intervention will likely be regarded as successful by clinicians if it is shown to be both efficacious and acceptable (that is, both co-primary outcomes are positive), so no penalty for multiple testing is needed to support this conclusion. In any case, the results of both hypothesis tests will be reported. No formal penalization for multiple hypothesis testing is planned for the subgroup or exploratory outcome analyses, which will be treated as exploratory and hypothesis-generating.

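### Does the lack of a stated alpha, and of a rule for a split result on the two co-primary outcomes, leave the no-penalty argument unsound?

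*Combined protocol and SAP*

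**What the plan says.** All references are to the combined protocol and SAP.

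- **Multiple hypothesis testing.** The premise is "The intervention will likely be regarded as successful by clinicians if it is shown to be both efficacious and acceptable", which the section equates with a positive result on both co-primary outcomes, "so no penalty for multiple testing is needed to support this conclusion". It then commits the authors to report both tests whatever they show.
- **Hypotheses.** Smartphone-linked patients are expected to have the larger mean SBP reduction at 6 months "compared to those who receive standard HBPM, and will be more likely to promote use of the device to a friend".
- **Primary outcome definitions.** Each outcome has its own purpose. For SBP: "The following pre-specified outcome will be used for the primary test of comparative effectiveness". For NPS: "The following pre-specified outcome will be used for the primary test of patient satisfaction".
- **Analysis Plan, Overview.** "Our primary analyses will test two independent hypotheses", each asking whether the arms differ on its outcome.
- **Subgroup analyses.** This section has the only explicit threshold: within-subgroup p-values are "reported only if the omnibus test is statistically significant at P<0.05". The NPS analysis specifies 95% confidence intervals.
- **Sample size justification.** "With 2000 patients randomized (1:1 ratio, 1000 standard vs. 1000 Smartphone-linked), we will have 80% power" for a difference of 0.125 SD, illustrated with SBP (SD 8, 11 against 10 mmHg). The section says openly that no power calculation was made for NPS.

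**The concern.** The waiver is argued for one conclusion only, that both outcomes are positive. It rests on a forecast of how clinicians will see the result and is not written as a decision rule. Elsewhere the two outcomes appear as separate tests of separate questions. If SBP were significant and NPS were not, one could argue from the outcome definitions that effectiveness had been shown, and from the multiplicity section that the intervention had not succeeded. With no stated alpha and no sentence on a split, that choice could seem open until the data are seen.

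The stake would be the error rate of the headline claim. If either test alone could count as success of the intervention, two unadjusted tests at 0.05 would carry a false-positive risk of nearly 10%, and the no-penalty argument would not cover that claim.

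**Working it through.** **1. Which alpha did the planners use?** Inputs from Sample size justification: 1000 per arm, 0.125 SD, 80% power. Power = Φ(0.125 × √(1000/2) − z), where z is the critical value.

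| Level | Power |
|---|---|
| two-sided 0.05 | Φ(2.795 − 1.960) = 79.8% |
| two-sided 0.025 | 71.0% |
| one-sided 0.05 | 87.5% |
| two-sided 0.01 | 58.7% |

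Only two-sided 0.05 gives the stated 80%. It also agrees with the 95% intervals for NPS. The level is unwritten but not in doubt.

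**2. How likely is a split?** P(exactly one positive) = p₁(1 − p₂) + p₂(1 − p₁) for independent test statistics. The 80% for NPS is assumed.

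- Power 80% each: 2 × 0.8 × 0.2 = 32%; both positive 64%; neither 4%.
- Correlated statistics (bivariate normal): both positive is 66.6% at correlation 0.3 and 68.7% at 0.5, so the split is 2 × (0.800 − 0.666) = 27% and 2 × (0.800 − 0.687) = 23%.
- NPS power 50%, independent: 0.8 × 0.5 + 0.2 × 0.5 = 50%.
- Only one effect real, with 80% power, counting significance in either direction: 0.8 × 0.95 + 0.2 × 0.05 = 77%. Here a split is usually the correct answer.

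**3. What error rate goes with each reading?**

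- Both required: a false success needs a false positive on at least one true null, and that test is run at 0.05. The rate is therefore at most 5%, or 2.5% if only results favouring the Smartphone arm count.
- Either suffices, both nulls true: 1 − 0.95² = 9.75% if independent, 9.1% at correlation 0.5.

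The second line matters only if the plan allows that reading. No section does.

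**4. Do the sections conflict?** The Overview and the outcome definitions assign one test to each question. The Hypotheses section supplies the direction, and testing a directional hypothesis two-sided is ordinary practice. The multiplicity section ties overall success to both outcomes. Read together, each test answers its own question, success of the intervention needs both, and a split is reported as a split.

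**5. Would an adjustment help?** At 0.025 per test, SBP power falls from 79.8% to 71.0%, and restoring 80% would take 1217 per arm instead of 1000. That price would protect against a claim the plan does not make.

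**The case for a change.** The strongest case is that a commitment to report both results is not a commitment on how to interpret them. A forecast of what clinicians will probably think does not bind the authors, and a plan that fixes a threshold for an exploratory subgroup test should fix one for its primary tests. NPS power is also unknown, and the missing-data section expects many NPS responses to be absent. A split could then be more likely than 32%: at NPS powers of 70%, 60% and 50% it is 38%, 44% and 50% under independence.

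It stands that no sentence states alpha for the primary tests and none prescribes the wording for a split. The rest carries less weight. Because both results must be published, a reader can always see that a single positive outcome fell short of the plan's own account of success. That removes most of the room for selective presentation.

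NPS power is a separate topic, and the plan is candid about it. Treating NPS as a mean of +100, 0 and −100, the detectable difference at 80% power is 2.8016 × SD × √(2/n). With n = 1000 per arm it runs from 8.3 points (assumed 70% promoters and 10% detractors, SD 66.3) to 12.5 points (assumed 50% and 50%, SD 100). Such a figure would inform a reader, but it only approximates the planned multinomial analysis, rests on assumed proportions, and alters nothing that will be done.

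**Conclusion.** The concern describes an omission of detail that analysts fill sensibly, not a flaw in the inference. The no-penalty argument is correct for the both-positive conclusion it names, with an error rate of at most 5%. Two-sided 0.05 can be recovered from the power figure (79.8% against a stated 80%) and the 95% intervals. The direction is given, and both results will be reported. The figure of nearly 10% belongs to an either-outcome success claim that appears nowhere in the plan.

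The split probability of 32% is correct arithmetic, but it assumes 80% NPS power and independent test statistics. Both outcomes come from the same patients, and the figure is 27% at an assumed correlation of 0.3 and 23% at 0.5. A sentence on alpha and on split results would only record what the sections already imply when read together. No test, estimate, interval or sample size would differ, so no change is called for.
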